7.4. Rasch-Built Overall Disability Scale (R-ODS)

The R-ODS consists of 24 items scored on a scale of 0 (unable to perform), 1 (able to perform, but with difficulty) or 2 (able to perform without difficulty). A total score will be calculated as the average of all non-missing items multiplied by 24 if at least 90% of the items are non-missing. The total score will be deemed as missing if more than 10% of the items (3 or more items) are missing.

7.5. Composite Autonomic Symptom Score-31 (COMPASS-31)

The COMPASS-31 questionnaire comprises 6 domains: Orthostatic intolerance, Vasomotor, Secretomotor, Gastrointestinal, Bladder, and Pupillomotor. Within each domain, individual questions are scored as follows: Simple yes or no questions are scored as 0 points for no and 1 point for yes. Questions about a specific site of symptoms or symptoms under specific circumstances are scored as 0 if not present and as 1 if present for each site or circumstance. All questions regarding the frequency of symptoms are scored as 0 points for rarely or never, 1 point for occasionally or sometimes, 2 points for frequently or “a lot of the time,” and 3 points for almost always or constantly. All questions regarding the severity of symptoms are scored as 1 point for mild, 2 points for moderate, and 3 points for severe. Questions assessing the time course of a symptom are scored 0 points for responses such as “gotten somewhat better,” “gotten much better,” “completely gone,” and “I have not had any of these symptoms,” 1 point for “stayed about the same,” 2 points for “gotten somewhat worse,” and 3 points for “gotten much worse.” The scores for changes in bodily functions depend on the individual question asked. For example, “I get full a lot more quickly than I used to when eating a meal” is scored 2 points and “I get full a lot less quickly than I used to” is scored 0 points, while the answer “I sweat much more than I used to” is given 1 point and “I sweat much less than I used to” is scored 2 points.

The overall scoring proceeds as follows:

- Sum the numerical values associated with responses in each domain
- Apply the following weighting factors to the domain sums:
 - Orthostatic intolerance, 4.0
 - Vasomotor, 0.83333333
 - Secretomotor, 2.1428571
 - Gastrointestinal, 0.8928571
 - Bladder, 1.1111111
 - Pupillomotor, 0.3333333

- Sum the weighted domain scores to obtain a total weighted score (maximum of 100)

Within each domain, there are “gatekeeper” questions. For example, consider questions 5-7:

5. In the past year, have you ever noticed color changes in your skin, such as red, white, or purple?

- 1 Yes
- 2 No (if you marked No, please skip to question 8)

6. What parts of your body are affected by these color changes? (Check all that apply)

- 1 Hands
- 2 Feet

7. Are these changes in your skin color:

- 1 Getting much worse
- 2 Getting somewhat worse
- 3 Staying about the same
- 4 Getting somewhat better
- 5 Getting much better
- 6 Completely gone

Answering “No” to question 5 obviates questions 6-7. Similarly, answering “Yes” to question 5 causes the responses to questions 6-7 to be summed in the resulting overall score. A failure to answer question 5 would render responses to questions 6-7 problematic. Question 5 is the gatekeeper question and question 6-7 will be referred as subsequent questions.

The full list of gatekeeper questions is:

- Question 1: Gatekeeper to questions, 2, 3, 4
- Question 5: Gatekeeper to question 7
- Question 16: Gatekeeper to questions 17, 18, 19
- Question 20: Gatekeeper to questions, 21, 22, 23
- Question 27: Gatekeeper to question 28
- Question 29: Gatekeeper to question 30

A domain score will be deemed as missing if:

- 1) Answering “No” or “Never” to gatekeeper question but non-missing responses to any of the subsequent questions.
- 2) Answering “Yes” to gatekeeper question but 1 or more missing responses to subsequent questions.
- 3) Missing response to gatekeeper question and 1 or more missing responses to subsequent questions.
- 4) Multiple responses to the same question within a domain, with the exception of question 6 that says “check all.”
- 5) Missing response to a question within a domain that is not part of a gatekeeper/ subsequent question set. These questions are: 8, 9, 10, 11, 12, 13, 14, 15, 24, 25, 26, 31. The exception is when both questions 9 & 10 are answered as “No” and question 11 is missing, the score will be 0.

When a gatekeeper question is missing response but all subsequent questions are non-missing, the gatekeeper question will be imputed as “Yes” or the max impairment (example:

“Constantly” for questions 27 and 29). For questions 9, 10, and 11, if both questions 9 and 10 are missing responses and the response to question 11 is “1,” question 9 & 10 will be imputed as “No.” For all other responses, question 9 & 10 will be imputed as “Yes.”

For each patient, if ≤ 2 domain scores are missing, the total score will be calculated by imputing the missing domain score by the average domain score using data from any of the patients who had non-missing score for that domain at the time point. If more than 2 domain scores are missing, the total score will be deemed as missing.

The full text of the COMPASS-31 is below.

1. In the past year, have you ever felt faint, dizzy, “goofy”, or had difficulty thinking soon after standing up from a sitting or lying position?
 - 1 Yes
 - 2 No (if you marked No, please skip to question 5)
2. When standing up, how frequently do you get these feelings or symptoms?
 - 1 Rarely
 - 2 Occasionally
 - 3 Frequently
 - 4 Almost Always
3. How would you rate the severity of these feelings or symptoms?
 - 1 Mild
 - 2 Moderate
 - 3 Severe
4. In the past year, have these feelings or symptoms that you have experienced:
 - 1 Gotten much worse
 - 2 Gotten somewhat worse
 - 3 Stayed about the same
 - 4 Gotten somewhat better
 - 5 Gotten much better
 - 6 Completely gone
5. In the past year, have you ever noticed color changes in your skin, such as red, white, or purple?
 - 1 Yes
 - 2 No (if you marked No, please skip to question 8)
6. What parts of your body are affected by these color changes? (Check all that apply)
 - 1 Hands
 - 2 Feet
7. Are these changes in your skin color:
 - 1 Getting much worse
 - 2 Getting somewhat worse
 - 3 Staying about the same
 - 4 Getting somewhat better
 - 5 Getting much better
 - 6 Completely gone

8. In the past 5 years, what changes, if any, have occurred in your general body sweating?
- 1 I sweat much more than I used to
 - 2 I sweat somewhat more than I used to
 - 3 I haven't noticed any changes in my sweating
 - 4 I sweat somewhat less than I used to
 - 5 I sweat much less than I used to
9. Do your eyes feel excessively dry?
- 1 Yes
 - 2 No
10. Does your mouth feel excessively dry?
- 1 Yes
 - 2 No
11. For the symptom of dry eyes or dry mouth that you have had for the longest period of time, is this symptom:
- 1 I have not had any of these symptoms
 - 2 Getting much worse
 - 3 Getting somewhat worse
 - 4 Staying about the same
 - 5 Getting somewhat better
 - 6 Getting much better
 - 7 Completely gone
12. In the past year, have you noticed any changes in how quickly you get full when eating a meal?
- 1 I get full a lot more quickly now than I used to
 - 2 I get full more quickly now than I used to
 - 3 I haven't noticed any change
 - 4 I get full less quickly now than I used to
 - 5 I get full a lot less quickly now than I used to
13. In the past year, have you felt excessively full or persistently full (bloated feeling) after a meal?
- 1 Never
 - 2 Sometimes
 - 3 A lot of the time
14. In the past year, have you vomited after a meal?
- 1 Never
 - 2 Sometimes
 - 3 A lot of the time
15. In the past year, have you had a cramping or colicky abdominal pain?
- 1 Never
 - 2 Sometimes
 - 3 A lot of the time
16. In the past year, have you had any bouts of diarrhea?
- 1 Yes
 - 2 No (if you marked No, please skip to question 20)

17. How frequently does this occur?
- 1 Rarely
 - 2 Occasionally
 - 3 Frequently _____ times per month
 - 4 Constantly
18. How severe are these bouts of diarrhea?
- 1 Mild
 - 2 Moderate
 - 3 Severe
19. Are your bouts of diarrhea getting:
- 1 Much worse
 - 2 Somewhat worse
 - 3 Staying the same
 - 4 Somewhat better
 - 5 Much better
 - 6 Completely gone
20. In the past year, have you been constipated?
- 1 Yes
 - 2 No (if you marked No, please skip to question 24)
21. How frequently are you constipated?
- 1 Rarely
 - 2 Occasionally
 - 3 Frequently _____ times per month
 - 4 Constantly
22. How severe are these episodes of constipation?
- 1 Mild
 - 2 Moderate
 - 3 Severe
23. Is your constipation getting:
- 1 Much worse
 - 2 Somewhat worse
 - 3 Staying the same
 - 4 Somewhat better
 - 5 Much better
 - 6 Completely gone
24. In the past year, have you ever lost control of your bladder function?
- 1 Never
 - 2 Occasionally
 - 3 Frequently _____ times per month
 - 4 Constantly
25. In the past year, have you had difficulty passing urine?
- 1 Never
 - 2 Occasionally
 - 3 Frequently _____ times per month
 - 4 Constantly

26. In the past year, have you had trouble completely emptying your bladder?

- 1 Never
- 2 Occasionally
- 3 Frequently _____ times per month
- 4 Constantly

27. In the past year, without sunglasses or tinted glasses, has bright light bothered your eyes?

- 1 Never (if you marked Never, please skip to question 29)
- 2 Occasionally
- 3 Frequently
- 4 Constantly

28. How severe is this sensitivity to bright light?

- 1 Mild
- 2 Moderate
- 3 Severe

29. In the past year, have you had trouble focusing your eyes?

- 1 Never (if you marked Never, please skip to question 31)
- 2 Occasionally
- 3 Frequently
- 4 Constantly

30. How severe is this focusing problem?

- 1 Mild
- 2 Moderate
- 3 Severe

31. Is the most troublesome symptom with your eyes (i.e. sensitivity to bright light or trouble focusing) getting:

- 1 I have not had any of these symptoms
- 2 Much worse
- 3 Somewhat worse
- 4 Staying about the same
- 5 Somewhat better
- 6 Much better
- 7 Completely gone

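### COMPASS-31 missing-domain rules discard domains that can be scored, including stray follow-up answers worth 0 points, and put other patients' average in the total

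*SAP*

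**What the plan says.** All of this is in SAP Section 7.5 unless stated otherwise.

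- **Gatekeepers.** In the worked example, 'No' "to question 5 obviates questions 6-7", while 'Yes' "to question 5 causes the responses to questions 6-7 to be summed in the resulting overall score". The printed form tells the patient to skip ahead after 'No' or 'Never' at Q1, Q5, Q16, Q20, Q27 and Q29.
- **Rule 1.** The domain score is missing after 'No' or 'Never' "to gatekeeper question but non-missing responses to any of the subsequent questions".
- **Rule 5.** The domain score is also missing if a question outside the gatekeeper sets is blank; Q31 is one of these. The only exception is Q9 and Q10 both 'No' with Q11 blank, which scores 0.
- **Filling the total.** With 2 or fewer missing domains the total is still derived, as follows: "imputing the missing domain score by the average domain score using data from any of the patients who had non-missing score for that domain". This is done separately for each assessment visit. Beyond that: "If more than 2 domain scores are missing, the total score will be deemed as missing".
- **Item scores.** "Simple yes or no questions are scored as 0 points for no and 1 point for yes". A frequency answer of 'Rarely' also scores 0. "Questions assessing the time course of a symptom are scored 0 points for responses such as" somewhat better, much better or completely gone. Severity starts at 1 point for mild.
- **Use.** Section 4.5 summarizes the total as observed value and change from baseline, and each domain score as a continuous variable. Section 3.10.1 carries the result of the partial imputation into all analyses.

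**The concern.** Rule 1 is a consistency check: the gatekeeper denies the symptom while a follow-up has been answered. It is reasonable when the two answers conflict, because the score is then unclear. But it fires on any answered follow-up, including one that adds nothing to the score. In that case the gatekeeper set scores 0 on either reading, and an effectively observed zero is replaced in the total by an average taken from other patients.

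Two features make this worse. Voiding applies to the whole domain, so in the gastrointestinal domain one stray diarrhea answer also removes the valid answers to Q12-15 and to the constipation set. And the same section scores Q9-11 as 0 when the symptom is denied and the time-course item is blank, but voids the domain for the same pattern in Q27, Q29 and Q31, with no reason given.

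At stake are individual COMPASS-31 totals and their changes from baseline, and the domain summaries, which lose these patients' scores.

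**Working it through.** **1. Domain maxima.** The SAP gives weights and item scores. The allocation of items to domains below is read from their content. Raw maximum x weight:

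| Domain | Items | Raw maximum | Weight | Weighted maximum |
|---|---|---|---|---|
| Orthostatic | Q1-4 | 1+3+3+3 = 10 | 4.0 | 40 |
| Vasomotor | Q5-7 | 1+2+3 = 6 | 0.83333333 | 5 |
| Secretomotor | Q8-11 | 2+1+1+3 = 7 | 2.1428571 | 15 |
| Gastrointestinal | Q12-23 | 4x2+10+10 = 28 | 0.8928571 | 25 |
| Bladder | Q24-26 | 3x3 = 9 | 1.1111111 | 10 |
| Pupillomotor | Q27-31 | 5x3 = 15 | 0.3333333 | 5 |

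The sum is 100, the SAP's stated maximum, which supports the allocation.

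**2. Where a stray answer can score 0.** A frequency or time-course follow-up can; a severity answer cannot. Zero-scoring stray answers are therefore possible after Q1, Q5, Q16 and Q20, but not after Q27 or Q29, whose only follow-ups (Q28, Q30) are severity items.

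**3. Orthostatic example.** Q1 'No' = 0; Q4 'Completely gone' = 0; Q2 and Q3 skipped.
- Stray answer ignored: 4.0 x 0 = 0.
- Stray answer summed: 4.0 x (0 + 0) = 0.
- SAP rules: domain missing, so the total receives 4.0 x the mean raw score of patients with data (weight: "Orthostatic intolerance, 4.0"). This is above 0 if any contributing patient has a symptom.

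The SAP gives no domain averages. Assuming 10%, 25% or 40% of the maximum, the patient gains 0.10 x 40 = 4, 0.25 x 40 = 10 or 0.40 x 40 = 16 points.

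**4. Gastrointestinal example.** Q16 'No' with Q17 'Rarely' (0 points). The rest of the domain can still score from 0 to 28 - 10 = 18 raw, or 18 x 0.8928571 = 16.07 weighted points. The fill is 2.5, 6.25 or 10 points under the same assumptions. With the 25% fill, the error runs from 6.25 - 0 = +6.25 to 6.25 - 16.07 = -9.82. It can go either way.

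**5. Pupillomotor example.** Q27 and Q29 'Never', Q28 and Q30 skipped, Q31 blank. The answered items give 0, and the blank item carries at most 3 x 0.3333333 = 1 weighted point. Rule 5 voids the domain and the fill is 0.10 x 5 = 0.5 to 0.40 x 5 = 2 points.

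**6. Group means.** The frequency of the pattern is not given. Shift in the mean total = share affected x points gained. Assuming 1-5% of patients, all with the orthostatic pattern: 0.01 x 4 = 0.04 to 0.05 x 16 = 0.8 points. Other domains have smaller maxima.

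**7. Change from baseline.** In the orthostatic case the error is upward at whichever visit it occurs. At a later visit only, it makes the change look worse; at baseline only, better; at both, it partly cancels.

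**The case against.** **A reader might infer that the section contradicts itself**, because follow-ups said to be irrelevant after 'No' can void the domain. The text does not support that. The worked example describes a correctly completed form; rule 1 deals with one that breaks the skip instruction. Treating conflicting answers as missing also fits Section 7, which treats multiple responses to a single-response question as missing.

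**A reader might infer that every 'No' with an answered follow-up has a true score of 0.** It does not. 'No' followed by 'Severe' is ambiguous: either answer may be the slip. The section itself reads completed follow-ups as evidence of symptoms when the gatekeeper is blank, imputing 'Yes' or maximum impairment. Scoring all such forms 0 would choose the most favorable value in an open-label study. Rule 1 should stay for these forms.

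**A reader might infer that real improvement is systematically erased.** The SAP does not show this. Q1, Q5, Q16 and Q20 ask about the past year, so a patient whose symptom resolved within it should answer 'Yes' and then 'Completely gone', and rule 1 does not fire. In the gastrointestinal domain the error has no fixed direction.

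**On Q31**, the form does send the patient there and offers a no-symptoms option, so a blank is a real omission. The same is true of Q11, which nevertheless has the exception.

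COMPASS-31 is also one of many descriptive measures, without hypothesis tests, and the recorded answers are listed. That limits the consequence but gives no reason to keep a rule that discards scorable answers.

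**Conclusion.** The point holds in a limited form. Rule 1 voids domains on stray answers worth 0 points, and rule 5 treats Q27, Q29 and Q31 differently from the parallel Q9-11.

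For an affected patient with at most 2 missing domains, an orthostatic score of 0 becomes 4-16 of 100 points in the total, if the average is 10-40% of the domain maximum. A gastrointestinal score can move either way, and the pupillomotor fill is 0.5-2 points. The fill is specified for the total only; the domain score itself stays missing.

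The averages and the 1-5% frequency are assumptions. The effect on group means is probably small: 0.04-0.8 points under those assumptions. A reader might add the orthostatic and gastrointestinal maxima (40 + 25) and conclude that 65 points could come from other patients. That would need the contributing patients to average the maximum in both domains, and nothing in the SAP suggests it.

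**What to change.** In Section 7.5:

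1. Limit rule 1 to stray follow-up answers that score above 0. When all stray answers score 0, score that gatekeeper set 0 and keep the rest of the domain as answered.
2. Leave truly contradictory forms, 'No' or 'Never' with a follow-up scoring above 0, as missing.
3. Extend the Q9-11 exception: with Q27 and Q29 both 'Never' and Q31 blank, score Q31 as 0.
4. Apply the same rules to baseline and post-baseline assessments, and list the inconsistent forms.
5. State whether Q6 counts as a subsequent question. The worked example names Q6-7 but the gatekeeper list names only Q7, so the reach of rule 1 after Q5 is unclear.

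The cost is a wording change and a small change to the scoring program. Under Section 3.4 the baseline can come from the parent study, so those baselines would need re-scoring under the same rules. An occasional mistaken 'No' will be scored 0; the listing shows where.

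### COMPASS-31 pupillomotor scoring: a blank Q31 voids a domain already fixed at 0, and no rule covers a blank severity item after a positive Q27 or Q29

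*SAP*

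**What the plan says.** SAP section 7.5 sums item points within each of six domains, weights the sums and adds them to a total with a maximum of 100. It then lists five conditions that make a domain score missing. Four matter here.

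- Condition 1: "Answering “No” or “Never” to gatekeeper question but non-missing responses to any of the subsequent questions".
- Condition 2: "Answering “Yes” to gatekeeper question but 1 or more missing responses to subsequent questions".
- Condition 3: "Missing response to gatekeeper question and 1 or more missing responses to subsequent questions".
- Condition 5: "Missing response to a question within a domain that is not part of a gatekeeper/ subsequent question set". The section continues: "These questions are: 8, 9, 10, 11, 12, 13, 14, 15, 24, 25, 26, 31". One exception follows: "The exception is when both questions 9 & 10 are answered as “No” and question 11 is missing, the score will be 0".

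The gatekeeper list names Q27 (for Q28) and Q29 (for Q30). In the questionnaire text both offer Never, Occasionally, Frequently and Constantly. The first option of Q29 reads "1 Never (if you marked Never, please skip to question 31".

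With up to two missing domains, each is filled with the average over patients who have that domain score at the time point. With more than two, the total is missing. Section 4.5 plans summaries of the COMPASS-31 total and of each domain, and section 3.10.1 carries the result of the partial imputation into all analyses.

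**The concern.** Two gaps affect Q27 to Q31.

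**Blank Q31 in a patient without eye symptoms.** Q31 asks for the course of the more troublesome of the two eye symptoms. If both are answered Never, there is no symptom to rate, and the other answers already imply a domain score of 0. Condition 5 nevertheless makes the domain missing. A known value is discarded, and the total receives an average that includes symptomatic patients.

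**Blank severity in a patient with eye symptoms.** Condition 2 is worded for Yes/No gatekeepers. Nothing in the list says what happens when Q27 or Q29 is answered Occasionally, Frequently or Constantly and the severity item is blank. Two competent programmers could score the same questionnaire differently, which a scoring appendix should prevent.

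**Working it through.** **Scale check.** Maximum raw points, from the scoring text and the response options, times the stated weights:

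| Domain | Raw maximum | Weight | Weighted maximum |
|---|---|---|---|
| Orthostatic intolerance | 10 | 4.0 | 40 |
| Vasomotor | 6 | 0.83333333 | 5 |
| Secretomotor | 7 | 2.1428571 | 15 |
| Gastrointestinal | 28 | 0.8928571 | 25 |
| Bladder | 9 | 1.1111111 | 10 |
| Pupillomotor | 15 | 0.3333333 | 5 |

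The sum is 100, as the SAP states. The pupillomotor domain has five items (Q27 to Q31) worth at most 3 points each, so it contributes at most 5 points to the total.

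**Blank Q31, with Q27 and Q29 both Never.**

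- Q27 and Q29 score 0. Q28 and Q30 are skipped by instruction.
- Had Q31 been answered with its no-symptom option, it would score 0 and the domain would be 0.
- With Q31 blank, condition 5 applies and the domain is missing.
- In the total, 0 is replaced by the domain average at that time point. The SAP gives no such average. Item scores are never negative, so it lies between 0 and 5 and the replacement cannot lower the total.
- One of the two permitted missing domains is used up.

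Compare Q9/Q10/Q11. There, too, two symptom questions are followed by one shared time-course question whose first option is that no symptom was present. When both symptoms are denied and the time-course item is blank, the SAP scores 0.

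**Blank Q28, with Q27 positive (Q30 after Q29 is alike).** Taking the conditions in turn:

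- Condition 1 needs No or Never at the gatekeeper: not met.
- Condition 2 needs Yes: Q27 has no such option.
- Condition 3 needs a blank gatekeeper: not met.
- Condition 4 concerns multiple responses: not met.
- Condition 5 does not list Q28 or Q30: not met.

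On a literal reading the domain is therefore not missing, and the sum runs over the responses given, so the blank adds nothing. Severity answers score 1, 2 or 3, so the shortfall per blank item is 1 × 0.3333 = 0.33 to 3 × 0.3333 = 1.00. With both blank it is 0.67 to 2.00, or 0.67/5 = 13% to 2.00/5 = 40% of the domain maximum.

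Examples:

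- Q27 Constantly (3), Q28 blank, Q29 Never (0), Q31 unchanged (1): 4 × 0.3333 = 1.33 literally. With Q28 answered, 5 to 7 raw points give 1.67 to 2.33.
- Q27 and Q29 Constantly, Q28 and Q30 blank, Q31 at its worst (3): 9 × 0.3333 = 3.00 literally. With both severities answered, 11 to 15 raw points give 3.67 to 5.00.

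If Yes in condition 2 is instead taken to mean any affirmative answer, the domain is missing in both examples and the total uses the average.

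**The case against.** *A blank Q31 is a real omission.* Q29 Never sends the patient on to Q31, which offers a no-symptom answer, so the blank is not an instructed skip. Condition 5 is also explicit and programmable. All of that is true. But a blank Q11 is equally an omission, with the same option available, and the SAP scores it 0. The two sets are analogous rather than identical: Q27 and Q29 are gatekeepers with their own follow-ups, while Q9 and Q10 are not. That difference does not weaken the inference to 0 when both are answered Never.

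*Condition 2 is clear in intent.* A reader might infer that the SAP scores a blank severity item as no severity. The document does not support that. It nowhere assigns 0 to a blank Q28 or Q30, and no severity answer is worth 0. The paragraph on missing gatekeepers pairs Yes with maximum impairment and gives Constantly as the example for Q27 and Q29, which favours reading Yes as any affirmative answer. What stands is that condition 1 was adapted to Never and condition 2 was not, so the case is unassigned.

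*A stated percentage inflation of the domain mean is not supported.* One might take p as the symptom-free share and q as their rate of blank Q31, and compute 1/(1 − pq) − 1. The SAP gives neither rate, and the formula assumes that symptomatic patients never leave Q31 blank. If they leave it blank at the same rate, and blanks are unrelated to their scores, the inflation is zero.

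*Voiding the domain may not be more accurate.* For a blank severity item, the all-patient average can lie further from the truth than the literal sum. That is correct, so extending condition 2 is justified by consistency with the other domains, not by shown accuracy.

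**Conclusion.** The point holds as two small defects in section 7.5.

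First, condition 5 discards a pupillomotor score already implied to be 0 when Q27 and Q29 are Never and Q31 is blank, contrary to the SAP's own treatment of Q9/Q10/Q11. Per affected assessment, the total rises by the domain average at that time point: between 0 and 5 of 100 points, actual value not given. The domain summary loses a zero, and one of the two allowed missing domains is consumed.

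Second, no condition assigns a blank Q28 or Q30 after a positive gatekeeper. Only on the literal reading is there an under-score, capped at 2.00 points; on the reading by intent the domain is missing. The finding is the ambiguity, not a rule that scores severity as zero.

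How often either pattern occurs cannot be judged from the SAP, so no overall bias in the domain or total means is claimed. All summaries are descriptive (section 3.2), COMPASS-31 is one of many efficacy scales, and no conclusion is shown to change. This is a desirable correction, not a critical one.

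**What to change.** Make two changes in SAP section 7.5.

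- Condition 5: add a second exception, parallel to the one for Q9/Q10/Q11. If Q27 and Q29 are both answered Never and Q31 is missing, Q31 is scored 0 and the domain is kept.
- Condition 2: extend it beyond Yes to any response other than Never for Q27 and Q29, so that a blank Q28 or Q30 after a positive answer makes the domain missing, as a blank follow-up does in the other gatekept domains.

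The cost is two wording changes and the matching lines of the scoring program. No new data are needed.

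### COMPASS-31 scoring (SAP 7.5): dryness reported as completely gone is imputed as two current symptoms, and question 6 is placed inconsistently

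*SAP*

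**What the plan says.** All of this is in SAP section 7.5.

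- **When a domain is missing.** Condition 5 covers "Missing response to a question within a domain that is not part of a gatekeeper/ subsequent question set". It enumerates the items: "These questions are: 8, 9, 10, 11, 12, 13, 14, 15, 24, 25, 26, 31". It then gives one exception: "The exception is when both questions 9 & 10 are answered as" No and question 11 is missing, in which case the score is 0.
- **Imputation of questions 9 and 10.** The paragraph after the conditions applies "if both questions 9 and 10 are missing responses and the response to question 11 is" 1: both become No. "For all other responses, question 9 & 10 will be imputed as" Yes.
- **What the items ask.** Questions 9 and 10 ask, in the present tense, whether the eyes and the mouth feel excessively dry. Question 11 reads "For the symptom of dry eyes or dry mouth that you have had for the longest period of time, is this symptom", with seven responses. Response 1 is that the patient has had none of these symptoms; response 7 is completely gone.
- **Scoring.** A Yes/No item scores 1 or 0. A time-course item scores 0 for completely gone. The secretomotor weight is 2.1428571.
- **Question 6.** The explanatory text says "Question 5 is the gatekeeper question and question 6-7 will be referred as subsequent questions". The list introduced as the full list of gatekeepers says "Question 5: Gatekeeper to question 7".

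**The concern.** A patient who leaves questions 9 and 10 blank and reports the dryness as completely gone is scored as having dry eyes and a dry mouth now. A resolved symptom then raises the COMPASS-31 score. If the pattern occurs at one visit and not another, the change from baseline moves for a reason unrelated to the patient's condition.

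The placement of question 6 is a separate defect. Conditions 1 to 3 for a missing domain depend on which items count as subsequent questions. Two programmers, one following the text and one the list, can score the same questionnaire differently. SAP section 4.5 summarizes both the COMPASS-31 total and its domain scores as efficacy results, so both defects reach reported tables.

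**Working it through.** **1. Check that the weights are read correctly.** Maximum raw points per domain come from the items and scoring text in section 7.5. The maximum of 2 for questions 8 and 12 comes from the examples given there.

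| Domain | Max raw | Weight | Weighted |
|---|---|---|---|
| Orthostatic intolerance | 10 | 4.0 | 40 |
| Vasomotor | 6 | 0.83333333 | 5 |
| Secretomotor | 7 | 2.1428571 | 15 |
| Gastrointestinal | 28 | 0.8928571 | 25 |
| Bladder | 9 | 1.1111111 | 10 |
| Pupillomotor | 15 | 0.3333333 | 5 |

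The sum is 100, the maximum the SAP states.

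**2. Secretomotor score with questions 9 and 10 missing and question 8 scoring 0.** Weighted score = (question 11 points + imputed points for 9 and 10) × 2.1428571.

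| Question 11 response | Q11 points | Imputed Q9 + Q10 | Weighted score |
|---|---|---|---|
| 1 none of these symptoms | 0 | 0 | 0 |
| 2 much worse | 3 | 2 | 10.71 |
| 3 somewhat worse | 2 | 2 | 8.57 |
| 4 about the same | 1 | 2 | 6.43 |
| 5 somewhat better | 0 | 2 | 4.29 |
| 6 much better | 0 | 2 | 4.29 |
| 7 completely gone | 0 | 2 | 4.29 |

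Response 7 scores the same as a symptom that is still present but improving. The 4.29 points are 4.29 / 15 = 29% of the domain. A patient who answers No, No and completely gone (question 8 again scoring 0) scores 0.

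**3. What response 7 supports.** Question 11 is about one symptom, the longest-lasting. If that one has gone, at most the other can remain. The supported contribution of questions 9 and 10 is therefore 0 or 1 × 2.1428571 = 2.14. The unsupported excess is 4.29 or 4.29 − 2.14 = 2.14.

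The true gatekeepers 1, 5, 16 and 20 do not have this problem. They ask about the past year, so Yes can be correct for a symptom that has since resolved.

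**4. Question 6.** The gatekeeper list covers 18 items: 1–4, 5 and 7, 16–19, 20–23, 27–28 and 29–30. Condition 5 covers 12. Together that is 30 of 31, and question 6 is the one left out. Three patterns show the consequence.

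| Pattern | Text (6 and 7 subsequent) | List (7 only) |
|---|---|---|
| Q5 No, both Q6 boxes ticked, Q7 blank | Domain missing (condition 1) | 2 × 0.8333 = 1.67 if Q6 is summed |
| Q5 Yes, no Q6 box, Q7 about the same | Domain missing (condition 2), if no tick counts as missing | (1 + 0 + 1) × 0.8333 = 1.67 |
| Q5 blank, no Q6 box, Q7 about the same | Domain missing (condition 3), if no tick counts as missing | Q5 imputed Yes; (1 + 0 + 1) × 0.8333 = 1.67 |

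With up to two domains missing, the total takes the all-patient mean of the missing domain. The SAP does not give that mean; for the vasomotor domain it lies somewhere from 0 to 5.

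**The case against.** **The two dryness rules can be reconciled.** A reader might infer that condition 5 and the imputation of questions 9 and 10 contradict each other. They need not. If condition 5 ran first, the imputation sentence could never take effect, so the only reading that gives both a meaning is to impute first. What is left is an unstated order and an odd result: one missing item loses the domain, while two keep it.

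**Yes to both is defensible for responses 2 to 6.** A reader might infer that question 11 supports at most one Yes. Its reference to the longest-lasting symptom allows for both, so it implies at least one. Yes to both follows the maximum-impairment convention used for gatekeepers in the same paragraph, and replacing it with a single Yes would be a preference. The argument does not extend to response 7, where the reported symptom is no longer present.

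**The score of 0 in condition 5's exception.** A reader might take this as the whole domain score, which would erase question 8. A domain score is defined as the sum of its responses, so the natural meaning is that question 11 scores 0. The wording is loose but not wrong.

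**Question 6 is a tick-all item.** Site questions score 0 or 1 for each site, so an unticked box already has a value, which may explain its omission from the list. That is fair, and it means a blank question 6 need not be missing. It does not remove the disagreement between text and list.

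**Small reach.** The patterns should be rare, and the analyses are descriptive with no hypothesis test. This stands.

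**Conclusion.** Two defects hold. First, imputing Yes to both items when question 11 is completely gone adds up to 4.29 of 100 points without support; the excess is 2.14 if the other dryness symptom is still present. Second, the SAP gives two accounts of question 6. They can change a vasomotor score by question 6's own contribution, up to 1.67 points, or turn the domain into a missing value that the cohort mean replaces in the total.

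These are per-record figures for specific response patterns. The documents give no frequency, so no effect on a group mean can be stated. The first figure assumes that the imputation runs before condition 5. If condition 5 applied instead, the record would take the cohort mean, and the difference would depend on a value that the SAP does not supply. The point is minor, but the scoring rule is wrong as written for response 7 and inconsistent for question 6.

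**What to change.** In section 7.5:

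1. Do not impute Yes to both for question 11 response 7. Either treat it like response 1 (No to both), which could under-score by 2.14 if the other symptom persists, or leave the domain missing under condition 5. State which.
2. Keep the existing rule for responses 2 to 6.
3. State that the imputation of questions 9 and 10 is applied before condition 5 and is an exception to it.
4. In the exception to condition 5, say that question 11 is scored 0.
5. List question 5 as gatekeeper to questions 6 and 7, and say whether no box ticked in question 6 after Yes to question 5 counts as missing or as 0.

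The cost is a few lines of SAP text and a small programming change. Any baseline COMPASS-31 record with these patterns, including one carried over from a parent study under SAP section 3.4, must be rescored so that change from baseline uses a single rule.
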